EPA regulates use of inert ingredients (also termed "other" ingredients) by toxicology profiles in animal tests and by their inclusion in EPA lists of "approved" other ingredients. The insect-repellent products proposed for testing have been tested on animals for potential oral and dermal toxicity. The active ingredient (Picaridin) has an extensive toxicity data file, has been previously registered by EPA and has a positive safety record in consumer use. MSDS files for the products we propose to test are appended.

6.1.8 Test Material Composition and Stability:

The test material formulations are typical of topical cosmetics and insect-repellent products marketed to consumers. They will be produced under applicable Good

Laboratory Practice standards, with records available to EPA. They will be couriered to Carroll-Loye Biological Research, with Chain-of-Custody documented. After that, they will be stored at the Carroll-Loye offices in a closed cabinet at room temperature (approximately 19-27°C). The Sponsor believes that the formulations will be stable for the duration of the study, based on previously conducted storage-stability studies. The EPA has extensive experience with enforcing requirements for such tests based upon their history with similar products applied to humans. Spectrum intends to provide any requested information as appropriate to safety and efficacy issues.

6.2. Negative Control:

6.2.1 Description of the Negative Control:

The negative control is untreated for both dosimetry and repellency assays. Each subject simultaneously serves as a treatment and control subject.

6.2.2 Rationale for Employing a Negative Control:

Dosimetry testing requires an untreated control for the assumption that dosimeters will not gain appreciable weight from contact with untreated skin.

The 'negative control' for efficacy data sets serves to insure that each tick employed in the study is attracted to the test subject before it is used in a repellency challenge. Ticks that fail to meet the questing criterion (§8.4.1) are not used against Test Materials. In this way the negative control serves as a pre-screening of the ticks, such that only actively questing ticks are then exposed to the treatments. Based on this manipulation of a standard control design, the crossing rate on the negative control is judged to be 100%.

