For efficacy testing of each test material, each subject is treated on an arm, and has the other arm untreated in order to assess the questing sufficiency of each tick prior to testing it on the untreated arm. The dosimetry study is an examination of dosing behavior for each test material. In that study, each subject will be treated, and will also serve as his or her own untreated control for the dosimeters.

8.2 Experimental Design:

The experiment will be partially randomized by subject. Because the treated condition will be evident to experimenters and subjects, and the test materials are readily distinguishable (opaque lotion versus clear, low-viscosity liquid), neither group will be effectively blinded. The obvious, relatively conservative criteria on which failure is will help to eliminate any influence of experimenter or subject bias.

8.3 Randomization Procedures for Repellent Efficacy Testing:

8.3.1 Allocation of subjects to treatment groups:

Subjects will be assigned to the treatment groups on the basis of a randomly assigned subject number. Subjects will be assigned treatment based on their subject number and the treatment allocation table, which follows.

8.3.2 Treatment allocation table:

Materials will be distributed among subjects as tabulated below. For simplicity, the model shows different set of subjects testing each repellent. However, individual subjects may test more than one repellent, on separate days.

Subject	Lotion	7% Pump	15% Pump
1	X		
2	X		
3	X		
4	X		
5	X		
6	X		
7	X		
8	X		
9	X		
10	X		
11		X	
12		X	
13		X	
14		X	
15		X	
16		X	
17		X	
18		X	
19		X	
20		X	
21			X
22			X

23			X
24			X
25			X
26			X
27			X
28			X
29			X
30			X

8.4. Conditional Boundaries or Limits of Study:

8.4.1. Ambient Host-seeking Pressure:

To be included in the test on a treated limb, each tick must first meet the crossing criterion on the untreated limb, following the procedure for the treated limb (§10.3.6), in the same test period.

8.5. Monitoring of Environmental Conditions During the Study:

Records will be made of environmental conditions (temperature, relative humidity, light intensity) at approximately 1-hour intervals throughout the data collection.

9 STUDY PROCEDURES:

9.1 Test Subjects:

9.1.1 Inclusion criteria, all subjects:

- 9.1.1.1 Age: 18-55 years
- 9.1.1.2 Sex: Male/female
- 9.1.1.3 Race: Any race
- 9.1.1.4 Written consent: (see 9.4, below)
- 9.1.1.5 Language: Speak and read English

9.1.2. Exclusion criteria:

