- 9.1.2.1 Known to be phobic of ticks.

- 9.1.2.2 Known to be sensitive or showing sensitivity to any of the test product ingredients after application.
- 9.1.2.3 Poor physical condition.
- 9.1.2.4 Unwilling to submit to brief query about personal condition.
- 9.1.2.5 Use of insect repellent within 1 day preceding the study.
- 9.1.2.6 Unwilling to refrain from use of perfumed products, alcoholic beverages or smoking after 9 p.m. the evening preceding the test and throughout the test.
- 9.1.2.7 Known to be pregnant or lactating. Pregnancy will be self-checked by each female volunteer on the morning of the repellent test using an OTC test kit provided by Carroll-Loye. Results of each such test will be immediately verified by direct inspection by a technician trained to make that assessment. Only volunteers scored as nonpregnant will be allowed to participate.
- 9.1.2.8 Unable to deliver the test materials or nymphal ticks to own left and right arms.
- 9.1.2.9 Unable to see nymphal ticks on skin or otherwise effectively monitor them on skin.
- 9.1.3.10 Student or employee of the Study Director.

9.1.3 Number of Subjects and Rationale for Sample Sizes:

In both dosimetry and efficacy testing, we will engage 10 subjects per treatment. Each subject is a replicate. It is possible that a single set of 10 individuals could complete all parts of the study. It is much more likely that substantially more than 10 individuals will participate.

The number of subjects is chosen as a compromise between several conflicting factors. In the absence of clear means of estimating the distribution of outcome values, it is difficult to predict an ideal sample size. From a strictly scientific standpoint, an appropriate response under such circumstances would be to increase the sample size, but ethical and economic considerations demand the opposite in

the present study, particularly during the efficacy testing phase.

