avoiding inaccuracy in this study. That position, coupled with the fact that data collection is only 'replicated' once (in a different habitat at that), argues for a prudent approach. To reduce the risk of over-representing atypically attractive subjects, as well the weight of the value obtained from any one subject, we regard 10 (rather than 6) treated subjects as a better sample size for the repellency portion of the study.

9.1.4 Individual subject influences on repellent performance and risks from participation, in relation to the choice of subjects:

Carroll¹ reviewed the factors that influence the performance of insect repellents and concluded that there is no *a priori* means of predicting an individual's attractiveness to a particular ectoparasite, or likely impact on a repellency trial's data set. Several studies have indicated that individuals differ in attractiveness to mosquitoes, for example, but individual attractiveness rankings shift substantially among parasite taxa. Skin-emanated volatiles influence attractiveness, as do skin temperature and absorption properties; these factors may likewise influence repellent efficacy.

On the other hand, it *is* clear that conditions of use strongly influence repellent performance. We intentionally test under conditions of light, temperature and humidity conducive to tick foraging behavior. Further, we expose subject individuals as uniformly as possible to the ticks, and have them handle the ticks in ways that minimally disrupt tick behavior. We also monitor subjects to prevent exposure of treated areas to external moisture or abrasion.

Analogous to the summation for repellency, there are few clear patterns permitting us to predict which individuals might be at relatively greater risk from participating in this study. Pregnant and lactating women are excluded on general medical principals, and persons over age 55 are excluded due to slightly elevated health risks from arthropod-borne diseases (see above), though the likelihood

of contracting the causal agent during a repellent test is very low.

9.1.5 Choice of subjects and recruitment:

9.1.5.1 Sampling Frame of Study Subjects:

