Data collection will take place in the main laboratory building and on the terrace of Carroll-Loye Biological Research in Davis, CA.

11 DATA ANALYSIS:

11.1 Experimental Unit:

The individual subject will be the experimental unit.

11.2 Replicates per Treatment:

For dosimetry, there will be 10 treated subjects. For efficacy testing, there will be 10 subjects treated with the test material and 2 serving as untreated controls, at each of 2 sites.

11.3 Statistical Methodology:

Statistics will be computed with SAS's JMP software, Version 5.0.1.2 (SAS Institute, Cary, NC).

11.3.1 Dosimetry:

Dosage will be calculated per square centimeter of skin. The amount of test material delivered to each dosimeter set in each trial will be calculated as:

weight after application – weight before application

The **total captured** by all treated dosimeters per trial will be calculated by adding the mass changes in all 4 dosimeters together, then subtracting or adding, respectively, any total weight gain or loss in the paired control dosimeters.

The **proportion covered** of the total limb surface area by the dosimeters is:

$$\frac{\text{Surface area of a set of 4 dosimeters}}{\text{Surface area of the limb}}$$

The estimated **dosage per trial** is:

$$\text{Total captured} \times 1/\text{proportion covered}$$

Subject means and standard deviations will be calculated for all measures of dosimeter weight changes as well as application behaviors (distance from nozzle to skin, number of pump actuations). We will use subject dose means for the test material to calculate the dosing grand mean (\pm SD). That mean, expressed as repellent weight per unit skin surface area, will be converted to volume and used to determine individual subject doses in the field repellency test. To accomplish that, the test material's specific gravity will be used to convert the dosage weight data to volumes, prepared for each subject on the basis of their skin surface area.

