Subject effects on dosing behavior will be examined with nonparametric tests for n - sample independent cases (Kruskal-Wallis tests). In multiple regression analysis, the average amount of test material intercepted by each subject's dosimeters, as well as dosing per unit of skin surface area, will be examined in relation to the distance from nozzle to skin, limb size and the number of times the pump was actuated. The relationship between dosing behavior and dosage will also be examined with Spearman-rank correlation tests.

11.3.2. Repellency:

Because all subjects use different ticks, all ticks are used only once, and neither organism interacts directly with conspecifics at the level of the skin and the repellent during data collection, we will analyze data by subject as independent, replicated values. The hypothesis that the test materials will significantly reduce the number of ticks Crossing treated versus untreated skin is *not* the focus of this study. The focus is to compute, for each test material, a reasonable estimate of mean and standard deviation for the duration between application and sufficient repellency breakdown such that two ticks crossing on a subject within a half hour period. That pattern is here assessed at a resolution of 15 minutes.

Complete protection time (CPT) is measured as the length of time from initial application to the First Confirmed Crossing. A FCC is a Crossing followed by another Crossing within 30 minutes. For example, a Crossing at 90 minutes followed by another at 135 minutes is not confirmed, but a third Crossing at 150 minutes would confirm that at 135 minutes, giving a CPT of 135 minutes.

CPT measured in this way will yield a single time value for each subject. Mean CPT will be calculated across all 10 subjects per treatment, and will be presented with standard deviation and 95% confidence interval information as well.

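### §11.2 states two sites and separate untreated-control subjects, against one laboratory, own-control subjects and 10 treated per product in the sections that define the design

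*Protocol*

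**What the plan says.** The data-analysis section sets replication for efficacy testing in §11.2: "there will be 10 subjects treated with the test material and 2 serving as untreated controls, at each of 2 sites".

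The sections that define the design read differently on three counts.

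- **Sites.** §4 places the study in the laboratory at the letterhead address. §10.4, shortly before §11.2, says "Data collection will take place in the main laboratory building and on the terrace" of that same facility. §12 lists one laboratory. No second site is named or described.
- **Controls.** §6.2.1: "Each subject simultaneously serves as a treatment and control subject". §8.1 treats one arm and leaves the other untreated for screening ticks. §11.3.2 again says that all subjects act as untreated controls.
- **Number treated.** §9.1.3: "In both dosimetry and efficacy testing, we will engage 10 subjects per treatment". It concludes: "we regard 10 (rather than 6) treated subjects as a better sample size for the repellency portion of the study". The allocation table in §8.3.2 has ten rows for each of three products, with no site column and no control-only rows. §11.3.2: "Mean CPT will be calculated across all 10 subjects per treatment".

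Some other text does suggest a field study or a second location. §9.1.3 describes the single replication of data collection as "in a different habitat at that", the schedule in §7.2 includes travelling to a field site, and §11.3.1 refers to a repellency test in the field. None of these gives another subject count or identifies a second site.

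**The concern.** §11.2 is where a reader looks for the replication of the study, and it cannot be followed together with the sections on treatment groups, controls, allocation and location. Someone planning recruitment from §11.2 would run twice as many treated sessions as §8.3.2 provides. They would also have to find untreated-only subjects who appear in no allocation table and no procedure. §9.1.3 argues that ethical and economic considerations weigh against a larger sample, particularly in the efficacy phase, so a doubled count is not a neutral slip. The data set is also meant for submission to the regulator, so the stated replication should describe the study actually run.

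**Working it through.** No power formula is involved: §9.1.3 sets the number of subjects by judgement. The check is a count, followed by a test of whether another reading removes the conflict.

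**1. The plan's own figure.** The §8.3.2 table has 10 rows for the lotion, 10 for the 7% pump and 10 for the 15% pump: 3 × 10 = 30 treated sessions. ("For simplicity, the model shows different set of subjects testing each repellent"; one person may in fact test several products on separate days, so these are sessions rather than distinct people.) This matches 10 per treatment in §9.1.3 and the divisor of 10 in §11.3.2.

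**2. The count under §11.2.**

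| | §8.3.2, §9.1.3, §11.3.2 | §11.2 as written | Ratio |
|---|---|---|---|
| Treated, per product | 10 | 10 × 2 sites = 20 | 2.0 |
| Untreated-only, per product | 0 | 2 × 2 sites = 4 | – |
| All, per product | 10 | 24 | 2.4 |
| Treated, three products | 30 | 3 × 20 = 60 | 2.0 |
| Untreated-only, three products | 0 | 3 × 4 = 12 | – |
| All, three products | 30 | 72 | 2.4 |

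The figures of 12 and 72 assume that control subjects are not shared between products, which the protocol does not state. The treated counts do not depend on this.

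**3. Readings that might remove the conflict.**

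- *The same 10 people are tested at both sites.* The number of people would not double, but sessions would. Each person would have two CPT values per product, whereas §11.3.2 takes a single value per subject and averages over 10.
- *The two sites are the laboratory building and its terrace.* §10.4 treats these as one facility and assigns no subjects to either. The count of 20 and the separate controls would remain.
- *The two sites stand for the two tick species in §6.4.* §11.2 says sites, and species would not explain separate untreated subjects.
- *The two controls are drawn from the treated ten.* Under §6.2.1 and §11.3.2 every subject is a control, not two of them.

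None of these fits.

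**4. The sample-size example in §9.1.3.** It cites a study of 8 subjects with mean 180 min and standard error 15 min, so SD = 15 × √8 = 42.4 min. With half-width 1.96 × 42.4/√N:

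- N = 10: 26.3 min, interval 154–206 (protocol: 155–205).
- N = 20: 18.6 min, interval 161–199 (protocol: 162–198).

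The protocol's rough figures are close to these. It shows N = 20 as an alternative, notes that ten more subjects shrink the interval no more than going from 6 to 10 did, and settles on 10. Twenty treated subjects per product, the total under §11.2, is thus a number that the rationale considered and did not choose.

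**The case against.** The strongest reply is that an analyst would not be misled. §11.3.2 fixes the CPT mean at 10 subjects per treatment, analyses data by subject, and has no site term; the same section says no statistical comparisons are planned. All of that stands. The primary analysis can be carried out as §11.3.2 writes it, and a careful reader can infer that 10 is meant.

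Four stronger readings are tempting, and the documents do not support them.

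- *A reader might infer that the untreated term in the Relative Protection formula is ambiguous.* It is not: §11.3.2 defines the measure as the treated arm relative to the untreated arm.
- *A reader might infer that §9.1.3 contradicts itself on replication.* Its statement that the study will not be repeated is limited to registration purposes, which is compatible with collecting data in two habitats within one study. The second-habitat remark is also offered as a reason for caution, so the choice of 10 does not depend on a second site.
- *A reader might infer that §11.2 promises the tighter precision of n = 20.* That needs the two sites to be pooled, which no section proposes; per site, n is still 10. The SD behind any such figure also comes from a cited mosquito study.
- *A reader might infer that §11.2 is the only stray text.* The field and second-habitat wording in §7.2, §9.1.3 and §11.3.1 shows that it is not.

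The reply narrows the consequence but does not remove the error. §11.2 and §11.3.2 are both current text, and they state different numbers of treated subjects.

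**Conclusion.** The contradiction is real and should be corrected before the study starts. §11.2 is incompatible with the design sections on sites (2 against 1), on controls (separate subjects against own control) and on treated subjects per product (20 against 10, or 60 against 30 sessions over three products). The error lies in the stated sample size and control structure, with consequences for recruitment and conduct. It does not change the CPT analysis in §11.3.2.

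This rests on taking "there will be 10 subjects treated with the test material and 2 serving as untreated controls, at each of 2 sites" at its plain meaning and as applying to each product, as its heading indicates. Carry-over from the companion field protocol SPC-001 is a plausible explanation, since the site questionnaire appended here bears that study's number and title, but this is an inference and the conclusion does not need it.

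**What to change.** Replace the efficacy sentence in §11.2 with wording to this effect: *for efficacy testing, 10 treated subjects per product at the one laboratory; each subject is his or her own untreated control for tick screening, using the untreated limb or portion of limb described in §10.3.6; there are no untreated-only subjects.* The reference to a portion of limb is needed because §10.3.6 allows for both arms being treated. A text that fixed the untreated arm as the control would create a new conflict.

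In the same edit, remove or reconcile the second-habitat remark in §9.1.3, the field-site travel in §7.2 and the reference to a field test in §11.3.1.

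The cost is amendment wording only. The number of subjects in §8.3.2, §9.1.3 and §11.3.2 does not change. §9.1.3 loses one supporting remark and keeps its other reasons for 10: less risk of over-representing atypical subjects, and less weight on any one value.

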The U.S. EPA has historically required a minimum of six subjects. Given that test repellents are nearly certain to exhibit greater than zero efficacy, and that testing is conducted under adequate ambient tick questing pressure, it is nearly certain that no untreated limbs will register fewer or later crossings than any treated limbs. Six is often regarded as a statistically sufficient sample for an observation set because the increment in the confidence of means estimate begins to drop off sharply at that point. Notably, under the historical guidelines, there seem to have been few problems with EPA registering repellents that commonly fail to meet their labeled performance specification.

The main scientific risk of using a very small sample, however, is that the probability of over-representing subjects inherently unattractive to ticks is rather large, as is the risk of substantial biasing from a single subject that generates unrepresentative values for undetected reasons. The fact that the study will not be replicated for registration purposes increases that risk substantially. Note that in our interpretation of the draft EPA guidelines, the response variable, Time to First Confirmed Crossing, is calculated as the average duration for all treated subjects. There is no consideration of variation. In any given study, increasing the number of treated subjects to 10 will improve the probability of accurately estimating the population mean.

The 95% confidence interval computation is useful for assessing the certainty of a means estimate, and for normal probability density function that interval is ± 1.96 standard error of the mean. In this study we anticipate that the distribution of Times to First Confirmed Crossings will be truncated toward the origin. Because available mean and variance data on

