Picaridin efficacy (e.g., Carroll¹) indicates that no individual values will be near zero, approximating the exponential model with the normal model is likely justifiable. Using the rule of thumb that a distribution in which the mean is greater than three standard deviations above zero may be regarded as effectively normal, it is sensible to compute and report the normal 95% confidence interval in this study. Alternatively, if tests indicate substantial deviation from a normal distribution, the deviation will be corrected prior to analysis. An exception would be cases in which there is frequent truncation of records ('data censoring') due to subject withdrawals before product failure. In that case, other means of analysis (Kaplan-Meier survival analysis, §11.3.1) will be employed, but that possibility is not strongly related to sample size considerations.

To consider an example, in a study of repellency employing 8 subjects, Cilek et al.² recorded a mean protection time of approximately 180 minutes, with a standard error of about 15 minutes. Had the N been 6, we can roughly predict that the 95% CI would be 148-212. At $N=10$, the estimate would be 155-205. At $N=20$, the interval would be roughly 162-198. Evidently, adding the additional 10 subjects to reach an N of 20 shrinks the interval, in absolute terms, no more than did the addition of 4 subjects to increase the sample size from 6 to 10.

To summarize, in the case of a highly efficacious repellent, adding subjects beyond 6 is likely to increase the precision of the means estimate only slowly. However, the regulatory justification for this study is predicated on an aversion to assuming that efficacy is closely predictable in new formulations. That conservatism is further justified on the basis of the individual and public health importance of

¹ Carroll, S. P. (2006) Evaluation of topical insect repellents and factors that affect their performance. Chapter 12 in *Insect Repellents: Principles, Methods, and Use*, Debboun, M., Strickman, D. and Frances, S. P. (eds.). Boca Raton, Florida, CRC Press.

² Cilek, J. E., Peterson J. L. and Hallmon, C. F. (2004). Comparative efficacy of IR3535 and DEET as repellents against adult *Aedes aegypti* and *Culex quinquefasciatus*. *J. Amer. Mosq. Control Assoc.* 20: 299-304

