We will employ a 15-minute exposure interval as a good minimum in terms of both the temporal resolution of the data set and subject ability to remain focused. Every 15 minutes, each subject selects an unused tick and tests it for active questing behavior as described. To initiate a screening or a repellent challenge, a tick is placed on the ventral arm or proximal palm, in the most hair-free portion, at the first (most distal line). Ticks are manipulated with the bristles of a fine artist's paintbrush. Ticks are placed so that they face the elbow. Ticks may be oriented to locomote toward the margin of the treated area with the gentle action of the paintbrush. Forearms should be held from approximately 30° to vertically above the lab bench surface if that increases the propensity of ticks to travel toward the body.

A crossing is scored if a tick travels at least 3 cm in a vector toward the elbow into the treated area (i.e., at least as far as the third line) within 3 minutes of beginning to move up the arm from the first line. A repulsion is scored when a tick changes its orientation away from, or parallel to, the margin of the treated area upon approach, or does not cross more than 3 cm toward the elbow within 3 minutes of entering the treated area.

Subgroups of approximately three subjects are led by a technician in the monitoring of time, ticks, and tick behavior. Time is monitored by referring to an electric chronometer with a highly visible display. The technician will record any crossings or repulsions as they occur. Repulsions are normally unambiguous reversals of direction. Subjects lift the tick off with the paintbrush after each assessment is complete. Any brushes that come into contact with a test material are discarded. Used ticks are immediately retired from the study by being transferred from the test arm to a container labeled "used".

Scientific Stopping Rule: Subjects are directed to cease tick exposures when a crossing is followed by another crossing within one-half hour, i.e., in either of the subsequent two exposure periods.

10.3.7 Forms for Retention of Source Data:

Dosimetry data will be recorded by a technician on a data form for each test formulation. Repellency data will be recorded by technicians on a repellency data form. Data forms are appended. The recording technicians sign and date the data forms.

10.4 Study Facility:

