The decision to calculate means, standard deviations and 95% confidence intervals is based on the requirements for such estimates in the EPA draft repellent efficacy testing guidelines (1999; OPPTS 810.3700). While EPA staff have indicated at recent HSRB meetings that those guidelines remain under development, they are the de facto standards at present. Accordingly, despite stark statistical weaknesses in making such estimates for samples as small as, e.g., 6 subjects, for consistency with acting standards, we include them. Note that no normalizing data transformations are appropriate in their estimation. Further, as no statistical comparisons are planned, there are no other contexts for normalizing repellency data in the proposed study. To partially ameliorate the shortcomings, our chosen sample size is 10 subjects, which will improve precision in estimating product performance. This sample, which is larger than that traditionally required by US EPA, is implemented at considerable expense to the study sponsor, but is consistent with suggestions from HSRB advisors to EPA.

To further improve the utility of the data set, we propose to use Kaplan-Meier estimates of the survival function of repellency with time since application (Complete Protection Time). Kaplan-Meier analyses provide median estimates with substantially reduced error estimates compared to means and standard deviations; in particular, they are much

less sensitive to data censoring. Moreover, they do not rely on assumptions of data normality.' Combining a much larger sample with the Kaplan-Meier estimate of repellent survival improves our ability to estimate the true temporal performance function of test materials in the population

12 STUDY LOCATION(S):

Carroll-Loye Arthropod Behavior Laboratory at the letterhead address.

.

13 QUALITY ASSURANCE:

A separate, professional Quality Assurance Unit (QAU) will inspect the study. The QAU will report to the Study Director. Protocol Review and Comments must take place before data collection commences. In-Life Inspection must include observing the measurement and recording of key variables by subjects and researchers. In addition, the Final Report will be audited for completeness and accuracy. A QAU Statement will address compliance and noncompliance or any omissions in auditing. Findings from the In-Life Inspection and the Final Report, as well as the QAU Statement, will be transmitted to the Study Director and to the Sponsor Monitor.

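### Section 11.3.2 averages CPT over all 10 subjects with no rule for a subject who never reaches a First Confirmed Crossing, and the Kaplan-Meier provisions do not close the gap

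*Protocol*

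**What the plan says.** Section 11.3.2 (Repellency) of the protocol measures CPT from application to the First Confirmed Crossing (FCC) and says "CPT measured in this way will yield a single time value for each subject". It states the aim as "a reasonable estimate of mean and standard deviation for the duration between application and sufficient repellency breakdown", and then: "Mean CPT will be calculated across all 10 subjects per treatment", reported with SD and 95% confidence interval.

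Section 10.3.6 gives the only scientific stopping rule: "Subjects are directed to cease tick exposures when a crossing is followed by another crossing within one-half hour". The visible text states no maximum exposure time. Section 9.1.5.3 allows withdrawal at any time.

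Censoring appears in two places:

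- Section 9.1.3 plans the normal-theory interval ("that interval is ± 1.96 standard error of the mean") and makes an exception for "frequent truncation of records ('data censoring') due to subject withdrawals before product failure". It continues: "In that case, other means of analysis (Kaplan-Meier survival analysis, §11.3.1) will be employed".
- The end of section 11.3.2 says "we propose to use Kaplan-Meier estimates of the survival function of repellency with time since application", with no condition attached. It explains that the mean, SD and interval are included for consistency with the regulator's draft guidelines.

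**The concern.** CPT is defined only by an FCC. A subject who leaves exposure without one is known only to have been protected up to the last challenge. The statement that each subject yields a single value is then untrue, and the mean over all 10 cannot be computed without a convention that the protocol does not give. The obvious convention, entering the last observed time as if it were a failure, pulls the mean down.

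The safeguards are incomplete. The switch in section 9.1.3 depends on the word *frequent*, which has no threshold, so the choice of summary could follow the data. It covers withdrawals but not subjects still protected when exposure ends. It also points to section 11.3.1, which is dosimetry. The later Kaplan-Meier proposal leaves the all-10 mean in place and does not say which result leads when they differ.

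Section 5.2 says the results will be the basis for accurate labelling, and section 6.1.1 bridges two of the three tested products to untested ones. An error in the lead figure would therefore carry beyond the products tested.

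**Working it through.** **Inputs.** The example in section 9.1.3 has 8 subjects, a mean of about 180 min and a standard error of about 15 min. The interval is mean ± 1.96 SE and n = 10 per product. The censored share is not given, so 10% to 50% is assumed.

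**The plan's own figures.** SD = 15 × √8 = 42.4 min. At N = 10 the half-width is 1.96 × 42.4/√10 = 26.3, giving 153.7–206.3 against the stated 155–205. With SD 40 (SE 14.1, still about 15) the intervals at N = 6, 10 and 20 are 148.0–212.0, 155.2–204.8 and 162.5–197.5. These match the stated 148–212, 155–205 and 162–198 to within 0.5 min. The example is reproduced.

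**Case A: subjects still protected at a common end of exposure C, entered at C.** With a = (C − 180)/42.4, the expected mean is 180·Φ(a) − 42.4·φ(a) + C·(1 − Φ(a)).

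- 50% censored: a = 0 and C = 180, so 90 − 42.4 × 0.399 + 90 = 163.1.
- 20% censored: a = 0.842 and C = 216, so 144 − 11.9 + 43.1, about 175.3.

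Simulation of 200,000 trials of 10 subjects from Normal(180, 42.4) gives:

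| Assumed share censored | C (min) | Mean (min) | Shift (min) | Interval width (min) | Coverage |
|---|---|---|---|---|---|
| 0% | – | 180.0 | 0 | 51.1 | 0.92 |
| 10% | 234 | 178.0 | −2.0 | 47.0 | 0.92 |
| 20% | 216 | 175.3 | −4.7 | 42.6 | 0.91 |
| 30% | 202 | 172.0 | −8.0 | 38.2 | 0.89 |
| 40% | 191 | 168.0 | −12.0 | 33.6 | 0.79 |
| 50% | 180 | 163.1 | −16.9 | 28.9 | 0.34 |

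The interval narrows by (51.1 − 47.0)/51.1 = 8% at 10% censored and by (51.1 − 28.9)/51.1 = 43% at 50%. The uncensored coverage is already only 0.92, because 1.96 is used with an SD estimated from 10 values. The loss due to censoring is the distance from 0.92, not from 0.95.

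**Case B: early withdrawals, times assumed uniform between 15 and 180 min, entered at withdrawal.**

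| Withdrawn of 10 | Mean (min) | Shift (min) | Interval width (min) | Coverage |
|---|---|---|---|---|
| 1 | 171.5 | −8.5 | 60.9 | 0.92 |
| 2 | 163.0 | −17.0 | 67.8 | 0.87 |
| 3 | 154.5 | −25.5 | 72.4 | 0.76 |

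The mean again falls, but the interval widens from 51.1 min.

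**Kaplan-Meier median in Case A.** Taken as the fifth ordered time, it averages 174.9 min uncensored and 174.9, 174.8 and 174.6 min at 10, 20 and 30% censored. At 30% it is reached in 95% of trials.

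**The case against.** The strongest reply is that the protocol already plans Kaplan-Meier without condition and calls it less sensitive to censoring. The two sections can be read together: Kaplan-Meier always, with the mean giving way when censoring is frequent. The mean is kept for a stated regulatory reason and its weakness is admitted. Section 9.1.7 enrols 3 alternates who may replace subjects withdrawing before useful data exist, which removes some of the earliest censoring. The bias understates protection, so it does not overclaim to users. Coding rules for censored times often sit in an analysis plan.

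Much of this stands, and it limits the point. It does not repair the protocol's own statements: that every subject has a CPT, that the mean covers all 10, and that only frequent withdrawals displace it. Alternates do not help with later withdrawals or with subjects still protected when exposure ends.

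A reader might infer more than the documents support:

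- *That censoring always shrinks the interval.* Case B, the only kind section 9.1.3 names, widens it.
- *That unfailed subjects are likely for the 15% products.* Section 5.1 expects reduced crossing for several hours, but no end of exposure or censoring rate is stated against which to judge this.
- *That coverage suffers badly at any censoring.* In Case A the loss at 20% is under one point, and the shifts at 20% and 30% are below the 15-minute resolution of the data.
- *That the Kaplan-Meier median cannot exist with 4 or fewer failures in 10.* If 4 subjects withdraw before any failure, 6 remain at risk and the third failure brings the estimate to 3/6 = 0.5.
- *That unfailed subjects would be dropped.* The protocol says all 10.
- *That the mean should be withheld.* Section 11.3.2 keeps it for consistency with the acting guidelines.

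**Conclusion.** The point holds in limited form. The protocol fixes a mean over 10 values that need not all exist, gives no rule for a subject without an FCC, and limits its switch to Kaplan-Meier by an undefined word and one cause of censoring, with a wrong cross-reference. If last observed times are entered, the mean is biased low under both patterns examined: by 2 to 17 min for 10% to 50% censored at a common end of exposure, and by 8.5 to 25.5 min for 1 to 3 early withdrawals among 10. The effect in the first pattern is small at 10% and becomes serious from about 30% to 40%. Narrowing of the interval belongs to that pattern alone.

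The sizes rest on a normal distribution with the example's mean and SD, on assumed censored shares, and on assumed withdrawal times. The example itself comes from a mosquito study of other repellents, so the minutes are illustrative. The direction of the bias in the mean does not depend on them.

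**What to change.** Amend sections 9.1.3 and 11.3.2 as follows:

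- Whenever any subject is censored, make the Kaplan-Meier estimate by product the headline CPT result: the median with its 95% confidence interval or, if the median is not reached, the proportion still protected at fixed hours with its lower 95% limit.
- Right-censor a subject without an FCC at the last completed challenge. Add a sensitivity analysis that counts an unconfirmed last crossing as failure.
- Keep the mean, SD and 95% interval as a secondary result for guideline consistency, and label the mean a lower bound when any subject is censored.
- Delete the condition that censoring be *frequent*, and correct the reference from 11.3.1 to 11.3.2.

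The cost is wording only, since Kaplan-Meier is already planned. The downside is that for a product with censored subjects the mean is no longer the lead figure.
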